### 16.2 Abnormal Clinical Laboratory Test Results

All clinically significant abnormal laboratory tests occurring during the study will be repeated at appropriate intervals until they return to baseline or to a level deemed acceptable by the Investigator and the Sponsor's clinical monitor (or his/her designated representative), or until the abnormality is explained by an appropriate diagnosis. Clinically significant abnormal laboratory tests that result in a change in study drug dosage, discontinuation of the drug, or require intervention or diagnostic evaluation to assess the risk to the subject, or are otherwise clinically relevant, should be recorded as AEs in the eCRF. Clinical diagnosis should be provided whenever possible. If no clinical diagnosis is available, the increase/decrease in the laboratory parameter may be recorded as an AE term. When an abnormal laboratory or test result corresponds to a sign/symptom of an already reported AE, it is not necessary to separately record the laboratory/test result as an additional event.

Laboratory abnormalities that do not meet the definition of an AE should not be reported as AEs. A Grade 3 or 4 event (severe), as per CTCAE, does not automatically indicate an SAE unless it meets the definition of serious as defined in the protocol and/or as per Investigator's discretion. A dose modification or medication for the laboratory abnormality may be required by the protocol in [Section 12.5.2](#) and should not contribute to the designation of a laboratory parameter abnormality as an SAE.

### 16.3 Abnormal Physical Examination Findings

Clinically significant changes, in the judgment of the Investigator, in physical examination findings (abnormalities) will be recorded as AEs and followed up until resolved or considered stable. Physical examination AEs should be followed up and reported in the same way as for the laboratory findings. Clinical diagnosis should be provided whenever possible. If no clinical diagnosis is available, the finding may be recorded as an AE term.

## 16.4 Pregnancy

In female subjects of childbearing potential, as well as all women <2 years after the onset of menopause, appropriate contraceptive measures are mandatory during the study (e.g., barrier method such as condoms or diaphragms; intrauterine devices; surgical methods; contraceptives of hormone preparations alone or in combination; or sexual abstinence).

Male subjects will use an appropriate method of contraception, such as vasectomy (confirmed to be azoospermia) or condom use.

In this study, contraception is required from the start of the study to 28 days after the last dose of the investigational product, regardless of gender.

Pregnancy itself is not an AE, but pregnancy-related AEs should be captured for study subjects and female partners of male study subjects who may become pregnant during the study. Pregnancies should be reported and followed up within the timelines specified for SAEs. Relevant risk factors as well as outcome should be recorded. Subjects should be advised to discontinue study treatment at the first suspicion of pregnancy.

## 16.5 Adverse Events of Special Interest

According to the Council for International Organizations of Medical Sciences (CIOMS VI) definition, an AESI is one of scientific and medical concern specific to the Sponsor's product or program, for which ongoing monitoring and rapid communication by the Investigator to the Sponsor can be appropriate. Such an event (serious or non-serious) might warrant further investigation in order to characterize and understand it.

Such events should be reported within the timelines and according to the procedures defined for SAEs.

Protocol-specific AESIs, e.g., psychiatric AEs, will be described in the statistical analysis plan (SAP). For cardiovascular disease-related AESIs, the diagnostic criteria are pre-specified in Appendix 5 of this protocol with conditions to ensure adherence to the diagnostic criteria standards across all centers in the study.

## 16.6 Serious Adverse Events

Information about all SAEs will be collected and recorded on the AE eCRF page. To ensure subject safety, each SAE must also be reported to the Sponsor within 24 hours of learning of its occurrence. All SAE will be followed until resolution or up to 30 days following the last infusion / last dose of study drug. An SAE is defined in general as an untoward (unfavorable) event that is serious and has the following outcome(s):

- Death
- Life-threatening: The study subject's life was in an immediate danger due to the event.
- Hospitalization: The study subject had to be hospitalized due to the event.
- Prolongation of hospitalization: The existing hospital stay had to be prolonged due to the event.
- Persistent/significant disability/incapacity: The event resulted in persistent/ significant disability/incapacity having caused long-term changes (either anatomical, physiological, or psychic) affecting the study subject's life.
- Congenital anomaly/birth defect: Any abnormalities in features or functions of the offspring of the study subject who has been exposed to study drug treatment during pregnancy.

- Important medical event: The event is considered medically significant, but none of the above categories are applicable (e.g., the study subject required medical intervention to prevent the event to become life-threatening). Important medical events are those which may not be immediately life-threatening or result in death or hospitalization but may jeopardize the subject or may require intervention to prevent one of the other outcomes listed above.

Hospitalizations occurring under the following circumstances are not considered SAEs: admission to a hospice for respite care; hospitalizations planned before entry into the clinical study; hospitalization for elective treatment of a condition unrelated to the studied indication or its treatment; hospitalization on an emergency, out-subject basis that does not result in admission (unless fulfilling the criteria above); hospitalization as a part of the normal treatment or monitoring of the studied indication; and hospitalization not associated with any deterioration in condition.

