## 8.1 Disease Progression/Withdrawal Criteria

The reason(s) for a subject discontinuing from the study will be recorded in the electronic case report form (eCRF). A discontinuation occurs when an enrolled subject ceases participation in the study, regardless of the circumstances, prior to completion of the protocol planned schedule. The Investigator must determine the primary reason for discontinuation.

Discontinuation from the study may occur for the following reasons:

- Disease progression;

For this study, disease progression will be defined as:

- Death due to any cause
- Development of secondary MF, as evidenced e.g. by bone marrow biopsy
- Transformation into acute myeloid leukemia or myelodysplastic syndrome, as evidenced by bone marrow biopsy

- Screening failure;
- Withdrawal of patient consent;
- Severe Noncompliance;
- Worsening of the underlying disease in cases when the further participation (with dose adjustment) is not expected to provide sufficient medical care to the patient;
- Study drug-related adverse event (AE) not recovering within the pre-specified period\*;
  - pre-specified period\*: 8 weeks after discontinuation of IMP administration
- Medical condition unrelated to the underlying disease or study treatment (study drug-unrelated AE);
- Lost to follow-up.

The EoT visit will be performed at the time of study discontinuation.

In case of early treatment discontinuation, the subject should be invited to attend the safety follow-up visit (28 days after the EoT visit).

Subjects who discontinue study drug due to a study drug-related AE or abnormal laboratory value must be followed at least once a week for 8 weeks (and subsequently at 2-week intervals) until resolution or stabilization of the event. If a subject has not recovered from any toxicity within 8 weeks of prematurely discontinuing study drug, s/he must be discontinued from the study, but will continue to be followed for toxicity as described above. In this case, data will not be entered into the database but will be documented in the study log, which is stored at the site.

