### **15.1.4 Safety Follow-up or End of Study Visit**

Subjects who discontinue study drug prematurely will return for a follow-up visit 28 days after the last dose. Please refer to the study flowchart and others (Appendix 1, Appendix 2, Appendix 3) for visit-specific assessments.

If subjects will participate in extension study of A19-201, safety follow-up will not be performed.

Subjects who discontinue study drug due to a suspected study drug-related AE must be followed at least once a week for 8 weeks and subsequently at 2-week intervals until resolution or stabilization of the event.

If a subject has not recovered from any toxicity within 8 weeks of prematurely discontinuing study drug, s/he must be discontinued from the study, but will continue to be followed for toxicity as described above.

Subjects who discontinue study drug due to a severe thromboembolic event will have an AE reported as the reason for discontinuation, and “severe thromboembolic event” indicated in the specific field.

If a subject has not recovered from any toxicity within 8 weeks of prematurely discontinuing study drug, s/he must be discontinued from the study, but will continue to be followed for toxicity as described above. In this case, data may not be entered into the database but will be documented in the study log, and stored at the site.

There may be a post-study care opportunity for study subjects who benefit from P1101 therapy. Further details will be provided as a separate protocol or amendment to this protocol at a later stage.

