### 16.1 Adverse Events

An adverse event (AE) is any untoward medical occurrence in a subject or clinical trial subject administered a medicinal product and which does not necessarily have a causal relationship with this treatment. All AEs occurring during the course of the clinical trial (i.e., from signing the informed consent form onwards through the treatment phase until the safety follow-up visit) will be collected, documented, and reported by the Investigator. Details on AE collection will be available in the eCRF collection guideline.

All AEs, serious and non-serious, will be fully documented on the appropriate eCRFs. For each AE, the Investigator will provide the onset, end, intensity, treatment required, outcome, seriousness, and action taken with the study drug. The Investigator will determine the relationship of the investigational drug to all AEs and record it in the eCRF. When assessing whether an AE is causally related to the study drug, the Investigator should consult the IB and use his/her clinical judgement and the subject's underlying disease before rendering an assessment.

All collected AEs will be coded according to the Medical Dictionary for Regulatory Activities (MedDRA). AEs and laboratory parameters will be graded according to CTCAE Version 5.0, (<http://ctep.cancer.gov>).

Adverse event monitoring should be continued until the safety follow-up visit/EoS or until AE resolution/stabilization, whichever occurs first. Safety follow-up visit is 28 days after end of treatment visit. AEs will be regarded as treatment-emergent if the time of onset or worsening is after or on the first intake of study drug.

Disease progression of PV should not be regarded or reported as an AE unless it is associated with a separate AE. Relationship will be assessed with not related, unlikely related, possibly related, probably and definitely related. Action taken will be described as dose increased, dose not changed, dose reduced, drug interrupted, drug withdrawn, and unknown.

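### Protocol 8.1 and 15.1.4 order follow-up of unresolved, treatment-stopping drug toxicities past week 8 but keep the later worsening, outcome and end date out of the analysis database

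*Protocol*

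**What the plan says.** Protocol 8.1 deals with a subject who stops study drug because of a drug-related adverse event or abnormal laboratory value. Such a subject "must be followed at least once a week for 8 weeks (and subsequently at 2-week intervals) until resolution or stabilization of the event". If the toxicity persists 8 weeks after stopping, the subject leaves the study and toxicity follow-up goes on, but "data will not be entered into the database but will be documented in the study log, which is stored at the site". Section 15.1.4 repeats the arrangement in different words: "data may not be entered into the database but will be documented in the study log, and stored at the site".

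The safety sections set recording duties and make no exception for this case:
- 16.1: "All AEs, serious and non-serious, will be fully documented on the appropriate eCRFs". For each event, "the Investigator will provide the onset, end, intensity, treatment required, outcome, seriousness, and action taken with the study drug". Section 15.3.11 likewise puts the stop date and outcome in the eCRF.
- 16.6: "Information about all SAEs will be collected and recorded on the AE eCRF page".

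The same two sections also limit follow-up:
- 16.1: "Adverse event monitoring should be continued until the safety follow-up visit/EoS or until AE resolution/stabilization, whichever occurs first".
- 16.6: "All SAE will be followed until resolution or up to 30 days following the last infusion / last dose of study drug".

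SAP 3.10.1 derives AE duration as end date minus start date. SAP 4.3.6.1 plans a table by maximum CTCAE grade and an overall summary with a row for AEs leading to death. It counts as treatment-emergent the AEs reported from first dose to 30 days after last dose, and it defines on-study deaths by the same 30 days.

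**The concern.** The protocol requires a site to collect the course of a toxicity and then directs that course into a log held at the site. The subjects affected are those whose drug-related toxicity both stopped treatment and failed to resolve, so the information lost concerns the most persistent events and is not a random subset. Safety is part of the primary objective (Protocol 6.1), and AE severity and events leading to permanent discontinuation are named safety endpoints (7.4). In a trial of 30 patients, one event that later worsens or proves fatal changes what a table shows. The wording also invites different practice between sites: *will not* in 8.1 is a ban, *may not* in 15.1.4 can be a ban or a permission, and neither section defines which data are meant.

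**Working it through.** The plan gives no figure on this point, so the check compares wording and time windows and then sizes the effect.

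**1. What the exclusion covers.** The sentence follows directly on the instruction to continue toxicity follow-up after study discontinuation. I read it as covering the follow-up data after week 8. Onset, grade, relatedness, seriousness and drug withdrawal would already be on the eCRF by then, with the outcome shown as not recovered.

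**2. Do the recording duties reach past week 8?** Count days from stopping the drug, taken as the day of the last dose. The 8.1 exclusion starts at 8 × 7 = day 56.

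| Rule | Window closes | Overlap with day 56 onward |
|---|---|---|
| 16.6, 30 days after last dose | day 30, which is 56 − 30 = 26 days earlier | none |
| 16.1, safety visit 28 days after last dose (15.1.1, 15.1.4) | day 28 | none |
| 16.1, safety visit 28 days after the end-of-treatment visit, itself held at study discontinuation (8.1) | 56 + 28 = day 84 | about days 56 to 84 |

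A direct conflict with 16.1 exists only in the last row. Section 16.1 itself counts the safety visit from the end-of-treatment visit, so that reading is available; 15.1.1 and 15.1.4 support the other.

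**3. Which outputs can change.**
- Maximum severity: the 30-day limit in SAP 4.3.6.1 decides which events count as treatment-emergent. No limit is stated for when the worst grade may occur. A Grade 3 event that becomes Grade 4 after week 8 is tabulated as Grade 3 if the later data stay in the log.
- Duration: SAP 3.10.1 needs an end date. SAP 4.3.1.6 completes partial end dates and SAP 4.3.1.5 plans no imputation of missing data. The longest events would therefore lack a duration. SAP 4.3.6.1 lists no separate duration table.
- AEs leading to death: the row has no stated time limit, but on-study deaths are limited to 30 days after last dose. Whether a death after day 56 belongs in the row is unclear.

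**4. Size for one subject.** 1/30 = 3.3 percentage points. If a fatal outcome after week 8 belongs in the death row (exact 95% intervals):
- left out: 0/30 = 0.0%, interval 0 to 1 − 0.025^(1/30) = 11.6%
- entered: 1/30 = 3.3%, interval 0.1% to 17.2%

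**5. How many subjects.** Protocol 5.3 reports 254 subjects randomized and 217 completing in PROUD-PV.
- Non-completers: 254 − 217 = 37; 37/254 = 14.6%; × 30 = 4.4. This mixes both arms and all reasons.
- The share with a drug-related toxicity unresolved at 8 weeks is not given. Assuming 10% to 50%: 4.4 × 0.10 = 0.4 and 4.4 × 0.50 = 2.2 subjects.
- Drug-related SAEs on P1101: 2. The arm size is not given; I assume 95 (P1101 subjects in the extension study) to 254/2 = 127. Then 2/127 × 30 = 0.5 and 2/95 × 30 = 0.6, before requiring that the event stop treatment and persist.

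**The case against.** The strongest reply is that the plan can be read coherently. AE data are entered up to the safety visit 28 days after last dose, an open event is entered as not recovered, and anything later goes to the site log. On that reading neither 16.1 nor 16.6 demands entry after week 8, and what remains is a choice of data cut-off. This stands as far as contradiction goes. A reader might infer from "Information about all SAEs will be collected and recorded on the AE eCRF page" that 16.6 flatly contradicts 8.1; the 30-day limit in the same section does not support that.

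A reader might also infer that the whole event disappears from the safety results. The documents do not support this either. The event would still be counted in the treatment-emergent, related, serious and discontinuation tables. SAE follow-up goes to the Safety Desk within 24 hours (16.7.1), reports are filed in the Trial Master File (16.7.2), and AESIs use the SAE procedures (16.5). The sponsor would know of a late change in a serious event or an AESI. The clinical database and the safety file could then disagree. For other non-serious toxicities no such route is stated.

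The death example is also open to challenge, since a death after day 56 falls outside the SAP's on-study deaths. The SAP does not tie the AE-leading-to-death row to that definition, so the example holds only conditionally.

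Finally, the frequency rests on assumptions. One of the two drug-related SAEs on P1101 in PROUD-PV was rheumatoid arthritis, which makes a persistent toxicity plausible, but Protocol 5.3 does not say that it stopped treatment or was unresolved at 8 weeks.

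What survives on every reading is that mandatory follow-up produces a grade, an outcome and an end date that the analysis will not contain. The documents give no reason for this.

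**Conclusion.** The point holds as a gap in the safety data, and the exclusion should be removed. It is a firm conflict between instructions only if the end-of-treatment visit is held at study discontinuation, and then for about days 56 to 84. The gap can understate maximum severity, leave the longest events without a duration and, depending on how the SAP row is read, omit a late fatal outcome (0/30 against 1/30). The number affected is small: 0 to 2 of 30, resting on the assumed 10% to 50% share of PROUD-PV non-completion, with zero possible. Two further assumptions apply: the excluded data are those after week 8, and sites record the event on the eCRF up to the cut-off. The sample size and the primary efficacy analysis are unaffected.

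**What to change.** **Protocol 8.1 and 15.1.4.** Replace the exclusion sentence with: *After discontinuation from the study, grade, seriousness, outcome and end date of that toxicity are entered on the AE eCRF page until resolution, stabilization or database lock; an event open at lock is entered as not recovered with the date of last contact.*

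**Protocol 16.1 (monitoring limit) and 16.6 (30-day limit).** Add to each: *except drug-related events leading to discontinuation of study drug, which are followed and recorded as specified in 8.1 and 15.1.4.* Without the exception in 16.1, the new entry duty would conflict with the limit there. The limits stay in force for all other events.

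**SAP 4.3.6.1.** State that the row for AEs leading to death counts treatment-emergent events with a fatal outcome whenever death occurs, and show on-study deaths (within 30 days of last dose) separately.

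**Cost.** One protocol amendment with two replaced sentences and two added clauses, and one clarification in the SAP. No visits are added, because the follow-up and its documentation at the site are already required. The AE page stays open longer for these few subjects; the rule for events open at lock keeps this from delaying database lock.

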## **16.7 Instructions for Expedited Notification of Serious Adverse Events**

### **16.7.1 Reporting Responsibility**

Any SAE occurring in a subject after providing informed consent and until completion of the last visit for subjects, e.g., completing EoS form must be reported to the sponsor. The period after discontinuing study drug may be extended if there is a strong suspicion that the drug has not yet been eliminated. All SAEs must also be reported for the period in which the study protocol interferes with the standard medical treatment given to a subject.

Each SAE must be reported by the Investigator to the Sponsor within 24 hours of learning of its occurrence, even if it is not considered to be treatment-related. Follow-up information about a previously reported SAE must also be reported to the Safety Desk within 24 hours of receiving it. The Safety Desk may contact the Investigator to obtain further information on a reported SAE. If warranted, an Investigator alert may be issued, to inform all Investigators involved in any study with the same drug that this SAE has been reported.

### **16.7.2 Reporting Procedures**

If the investigator becomes aware of a serious adverse event or malfunction of device, the investigator must report it to the point of contact described in “4) Contact Information for serious adverse event” in the Attachment 1 of the protocol by telephone, fax or e-mail, etc. within 24 hours.

If additional information such as follow-up information is collected, it should be reported immediately to the sponsor. All the reports will be filed in the Trial Master File.

## **17 STATISTICAL ANALYSIS**

### **17.1 General Consideration**

Categorical variables will be summarized using frequency counts and percentages. Percentages will be presented to 1 decimal point, unless otherwise specified. Continuous variables will be summarized by total number (n), mean, standard deviation, median, minimum, and maximum.

### **17.2 Sample Size Estimation**

Sample size is calculated, based on the following assumptions;

- The target population of the Japanese local study: Japanese PV patients for whom the current standard of treatment is difficult to apply.
- Study design: P1101 single arm no controlled study (previous proposal was designed as a historical control study using PROUD-PV study).
- Primary study objective: To evaluate the safety and efficacy of P1101 for Japanese PV patients for whom the current standard of treatment is difficult to apply.
- Primary efficacy variable: Complete Hematological Response (CHR)

- Study period and evaluation visits: 3 month, 6 month, 9 month and 12 months. The safety follow-up will be continued to 12 months and the major efficacy data will be obtained at 12 months.
- The primary analysis of the primary endpoint: The lower limit of the 95% confidence interval of CHR rate is greater than 11%, and also the slope of the linear regression model of the CHR rate time course is greater than 0 (positive trend):
- The rationale: the natural healing rate (placebo response) of CHR rate of PV patients is 0%, thus if the lower limit of 95% confidence interval of the CHR rate exceed 11%, the efficacy of P1101 can be confirmed. The rationale to set the CHR rate limit as 11% is, (1) 11% is the minimum CHR rate value of P1101 obtained in the PROUD-PV study, (2) and the trend of the CHR rate is positive, thus 11% can be considered as a limit of the acceptable clinical risks.
- Assuming the above conditions, the power of the study at 9 months will be about 85% with 25 cases (CHR rate of the PROUD-PV study at 3, 6, 9, and 12 months are 11%, 27%, 36% and 43%, respectively). Considering the uncertainty of maximum 5 patients who are different background from PROUD-PV, a total of 30 cases will be reasonable to evaluate both efficacy and safety.

